## Preliminary title:

The effects of 6 months dietetic counselling in clinical care on the cardiometabolic risk profile and diet quality of cardiovascular patients.

## 1. Introduction

This data analysis plan (DAP) is developed to guide the statistical analysis of the Voed je Beter trial data. The DAP provides detailed information of the populations that will be analyzed, the parameters that will be evaluated and the specific statistical methods that will be applied. This version of the DAP is designed to evaluate the primary outcome of the trial: the difference in 10-year recurrent cardiovascular risk (%) between the two study arms. For the secondary outcomes, separate DAPs will be created.

### 1.1 Role of the funding sources

The sponsors of the study had no role in study design, data collection, data analysis, data interpretation, or writing of the report. The corresponding author had full access to all the data in the study and had final responsibility for the decision to submit for publication.

## 2. Protocol summary

### 2.1 Development of protocol

The Voed je Beter trial is registered at clinicaltrials.gov as study NCT05071092 (see <https://classic.clinicaltrials.gov/ct2/show/NCT05071092>). The original protocol was approved by the Medical Ethical Committee (NL73021.091.20), in December 2020, and underwent minor changes since then that were all approved by the Medical Ethical Committee. All participants provided written informed consent.

### 2.2 Rationale

For individuals with a diagnosis of cardiovascular disease (CVD), the estimated five-year rate of experiencing recurrent myocardial infarction, stroke, heart failure, or cardiovascular-related death is 20-30%(1). The risk of getting a cardiovascular event is five times higher in people with CVD compared to those without CVD (1). Lowering the probability of recurrent cardiovascular events in patients with known CVD is referred to as secondary cardiovascular prevention. Secondary cardiovascular prevention consists of both medication use and behavioral strategies for risk factor management, including lifestyle interventions like smoking cessation, physical activity and healthy diet.

Many risk factors for CVD are closely linked to diet, including high blood pressure, high low-density cholesterol (LDL), low high-density cholesterol (HDL), and type 2 diabetes. Substantial evidence from prospective cohort studies shows that higher diet quality is associated with a 14–29% lower risk of CVD and 0.5–2.2 years greater CVD-free survival time (2, 3). Furthermore, the PREDIMED trial showed that

adhering to a Mediterranean diet resulted in less cardiovascular events (myocardial infarction, stroke or death from cardiovascular causes) compared to a control diet (4). However, whether such dietary interventions are equally effective in secondary prevention, has been less well researched.

The large CORDIOPREV trial showed that adhering to a Mediterranean diet appears to be beneficial for people with CVD. In this trial in which more than 1,000 Spanish CVD patients participated, the group that followed a Mediterranean diet appeared to have a 25-30% lower risk of a cardiovascular event (5). It must be noted here that the CORDIOPREV study was conducted in a Mediterranean country with a high acceptance for the Mediterranean lifestyle intervention. It can be questioned if dietary interventions are effective in clinical practice, where cardiovascular patients are not always adequately guided in adjusting their diet. It is well known that adhering to a healthy dietary pattern is difficult (6, 7). There is need for more research that confirms the effectiveness of dietary interventions in secondary prevention of CVD in a clinical care setting.

Besides the Mediterranean diet, dietary patterns with high diet quality are known to be beneficial for CVD risk factors. Especially increasing dietary fiber and reducing salt intake have the potential to improve the risk profile and lower the risk of recurrent CVD. Increasing dietary fiber intake is associated with reductions in low density lipoprotein (LDL)-cholesterol levels (8) and even modest reductions in salt intake cause important reductions in blood pressure (9). An intervention that focuses on improving fiber and salt intake could therefore potentially reduce the risk of recurrent events.

However, to investigate this, it is important to not only look at individual risk factors, but at their combination. It is precisely about the presence of a combination of risk factors that determine the cardiovascular risk profile. To assess individual risk profiles, prediction tools can be used. The SMART (Second Manifestations of Arterial Disease) risk score takes into account multiple risk factors and is designed to estimate the 10-year risk for myocardial infarction, stroke or vascular death in individual patients with clinically manifest atherosclerotic vascular disease (10).

To assess the impact of incorporating dietary changes alongside medication on the risk of cardiovascular disease in cardiovascular patients, we performed a randomized controlled trial in a Dutch health care setting. By doing so, we also aimed to investigate whether it is possible to better implement dietary counselling in the current care pathway for people with CVD.

## 2.3 Objective

With the Voed je beter trial, we aim to investigate the effects of dietetic counselling in clinical care on the cardiometabolic risk profile and diet quality of patients with established CVD. The dietary counselling focused on improving the adherence to the Dutch dietary guidelines.

## 2.3 Population

Study participants were identified and recruited from two hospitals in the Netherlands (Gelderse Vallei, Ede and Rijnstate, Arnhem, the Netherlands). Eligible for participation were individuals with a

diagnosis of cardiovascular disease, including acute coronary disease syndrome, angina, coronary revascularization, TIA or stroke, symptomatic aortic iliofemoral atherosclerosis, aortic aneurysm, intermittent claudication, or peripheral revascularization. Patients were excluded from participation if they were <18 years old, used medication for the treatment of diabetes, had a known hereditary form of CVD, had an eGFR <30ml/min, were participating in another study that interfered with the outcomes of the current study, or were not able to speak and understand Dutch.

## 2.4 Design

The Voed je Beter trial is a multicenter, randomized, controlled trial with two parallel arms. Patients were randomly assigned in a 1:1 ratio to usual care or the intervention group. The allocation sequence was computer-generated using block-randomization with variable block sizes (4, 6, 8). Allocation was stratified by hospital.

The intervention period was set at six months. Patients in the intervention group were referred to a dietitian close to their home address or, if that was not available, an online dietitian practice. Patients met with the dietitian seven times within six months with a maximum of 5 clock hours in total. Dietitians were instructed to guide the patients in improving adherence to the Dutch Dietary Guidelines (11). The Dutch Dietary Guidelines include recommendations on 16 components, including salt, vegetables, fruit, whole grain products, legumes, nuts, dairy, fish, tea, fats and oils, coffee, red meat, processed meat, sweetened beverages and fruit juices, and alcohol. Together with the dietitian, patients chose themselves which components they were going to improve. The diet in the study was therefore not prescriptive; goals were negotiated individually with each participant during their first session with the dietitian and were reviewed at each visit. Dietitians were instructed to at least set a goal on improving the intake of salt, fruit or vegetables as these are hypothesized to be the most relevant components for patients with cardiovascular diseases. Due to the nature of the intervention, blinding of dietitians, researchers, and patients was not possible. To limit bias during data analysis, an independent researcher will recode the groups in a way it is no longer possible to determine which group is intervention and which is control. The unblinding of the groups will take place after analyzing the primary outcome.

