## 2.8 Secondary endpoints

As secondary outcomes, changes in LDL-cholesterol, body weight, CRP and systolic blood pressure will be presented and compared between groups. Similarly, the change in proportion of individuals using lipid lowering agents, antiplatelet or anticoagulant agents, or blood pressure lowering agents will be presented and compared between groups.

Changes in diet quality, as assessed with the Dutch Healthy Diet index, will be presented for the total population and for the two groups separately but will not be compared with statistical tests. Changes in smoking habits will be presented for the total population and for the two groups separately as % of individuals smoking at baseline and at 6 months.

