#### 4.5 Data distribution and model checking

Analysis of covariance (ANCOVA) will be used to compare continuous data between the intervention and control group. For the primary outcome, SMART risk score at 6 months is considered the dependent variable, and the categorical grouping variable (intervention or control) will be added as independent variable. As covariates, the SMART risk score at baseline and hospital will be added. The ANCOVA model will be implemented using the `lm` function in R. Assumptions of homogeneity of regression slopes and homogeneity of variances will be checked with the imputed data sets.

For comparison of changes in LDL, body weight, CRP and systolic blood pressure, similar ANCOVAs will be performed with adjustment for study site and baseline values.

Chi-Square tests will be used for the analysis of medication use as this is presented as dichotomous data. The 95% CI will be presented for the difference in proportions. If expected cell frequencies are less than 5, Fisher's exact tests will be used.

If the assumptions underlying ANCOVA (normal distribution of residuals, homogeneity of variances) are not satisfied, data will be transformed. If data is still not normally distributed, linear mixed models will be used. This model will include fixed effects for the SMART risk score, and a random intercept for the grouping variable to account for individual variability within each group. The models will be implemented using the '`lme4`' package in R.

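### Section 2.4 lets the group code be broken once the primary outcome is analysed, so masking is not guaranteed for the 6-month secondary comparisons, and section 1 leaves unclear which plan governs them

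*SAP*

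**What the plan says.** Section 2.4 states that "blinding of dietitians, researchers, and patients was not possible". It then introduces a substitute at the analysis stage: "To limit bias during data analysis, an independent researcher will recode the groups", so that the intervention arm cannot be told from the control arm. The end of that masking is set by one event: "The unblinding of the groups will take place after analyzing the primary outcome".

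Section 1 describes the scope of the document: "This version of the DAP is designed to evaluate the primary outcome of the trial". It continues: "For the secondary outcomes, separate DAPs will be created". No date is given for those plans, and no condition relative to unblinding.

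Two later sections nevertheless deal with secondary outcomes. Section 2.8 says that "changes in LDL-cholesterol, body weight, CRP and systolic blood pressure will be presented and compared between groups", and that use of three classes of medication will be compared too. Section 4.5 supplies the methods. For the four continuous outcomes, "similar ANCOVAs will be performed with adjustment for study site and baseline values". For the medication classes, "Chi-Square tests will be used for the analysis of medication use as this is presented as dichotomous data", with Fisher's exact test when expected counts are small. Diet quality and smoking are described without tests.

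In section 5, the shell of Table 2 shows systolic blood pressure, LDL-cholesterol and body weight by Group A and Group B, and Table 3 does the same for diet quality.

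**The concern.** Staff and patients knew the allocation during the trial, so the recoded labels are the only protection against analysis decisions that lean towards one arm. Section 2.4 guarantees that protection for the primary outcome and for nothing else.

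Two features make this worth settling. First, section 2.7 computes the 6-month risk from the baseline risk and the changes in LDL-cholesterol and systolic blood pressure. An analyst who has seen the primary result by arm therefore already knows a good deal about two of the secondary outcomes. Second, if the secondary outcomes really belong to plans still to be created, as section 1 says, those plans could be written or finalised with the arms and the primary result known. A reader of the eventual report could not tell from this document whether section 4.5 or a later plan was binding for LDL-cholesterol, blood pressure, weight, CRP and medication use.

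**Working it through.** The plan states no figure on this point, and the point is about the order of steps. The check is to set the sections side by side.

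**Step 1: what masking covers**

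| Question | Where | Answer |
|---|---|---|
| What is the recoding for? | 2.4 | Limiting bias in data analysis, not restricted to one outcome |
| When may the code be broken? | 2.4 | Once the primary outcome is analysed |
| Is release tied to the secondary analyses or their plans? | 1, 2.4, 2.8, 4.5 | No |
| Are secondary results laid out under coded labels? | 5, Tables 2 and 3 | Yes for blood pressure, LDL-cholesterol, body weight and diet quality |
| Are CRP and medication use in those tables? | 5, Tables 2 and 3 | No |

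The purpose and the table layout point towards masked secondary analyses, but the release rule does not secure them. The outcomes compared in 2.8 number 4 continuous + 3 medication classes = 7. Table 2 shows 3 of these 7 by coded group. CRP and the three medication classes have no coded shell.

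**Step 2: which plan governs**

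| Item | Section 1 | Sections 2.8 and 4.5 |
|---|---|---|
| LDL-cholesterol, body weight, CRP, systolic blood pressure | Left to separate plans | ANCOVA adjusted for site and baseline |
| Use of three medication classes | Left to separate plans | Chi-square or Fisher's exact test |
| Diet quality | Left to separate plans | Descriptive, no test |

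Both columns cannot be the rule for the same outcomes.

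**Step 3: what remains open at the time of unblinding**

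- Section 4.5 fixes the outcomes, the covariates and the first-line tests.
- It calls for transformation if the ANCOVA assumptions fail, but names neither a criterion for failure nor a transformation. CRP is the clearest case: section 2.7 enters it into the risk score as a logarithm, while 4.5 plans an ANCOVA like that for the other outcomes without saying on which scale.
- The mixed-model fallback is written in terms of the SMART risk score. No fallback is spelled out for the four secondary outcomes.
- Data collected under section 2.5 but not analysed here (the 3- and 12-month visits, urine measures, nutritional biomarkers) depend wholly on plans not yet described.

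**Step 4: effect on the primary analysis**

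There is none. The primary outcome is analysed under the code. The sample size in section 2.9 does not depend on the timing of unblinding. As a check on it, a difference of 3.3 with SD 6.3 at two-sided 0.05 and 80% power needs 58 per group by the normal approximation, against the stated 57. Power at 57 per group is 79.9%. Allowing for 20% dropout, 57 / 0.80 = 71.25, rounded up to 72 per group, or 2 × 72 = 144 as stated.

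**The case against.** The strongest reply is that the secondary methods are largely settled. Section 4.5 gives the model, covariates and tests for all seven comparisons, and any transformation is triggered by assumption checks, not by the result. This largely stands. It limits the exposure to the unspecified steps in 4.5 and to whatever later plans may add.

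A second reply is that masking the primary analysis alone is a legitimate choice in an open trial. That is fair as a matter of design, but the plan's stated aim and its coded tables go further than its release rule does.

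Three stronger readings are tempting and are not supported:

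- *That the secondary results will be produced after unblinding.* No section says so. The text is silent on the order, and the Group A/B shells suggest coded production.
- *That the later plans will replace section 4.5.* The document does not say this. Those plans may concern other time points and biomarkers, and their dates and contents are not available.
- *That the false-positive rate rises by a known amount.* If an analyst could choose the best of 2 to 4 versions of an analysis with test statistics correlated 0.6 to 0.9 (assumed values), the two-sided error would be roughly 7% to 14% instead of 5%. But a two-sided test gives the same p-value whichever group is called A. An analyst working with coded labels could make the same selection, so this inflation is not caused by breaking the code and should not be charged to it.

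**Conclusion.** The point holds as a gap in the rule and a conflict of scope. Section 2.4 does not guarantee masking for the 6-month secondary comparisons, and section 1 disagrees with sections 2.8 and 4.5 on which plan governs them. The text permits some secondary choices to be made knowing the arms and the primary result; it does not show that this will happen.

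No numerical size can be put on it. Severity is minor: a cheap improvement that makes the recoding serve its declared purpose. The conclusion rests on this document alone and assumes that no other trial document fixes the order of unblinding and secondary analysis.

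**What to change.** In section 2.4, replace the unblinding rule with: *The code is broken only after the primary outcome and all 6-month secondary intention-to-treat comparisons listed in section 2.8, including CRP and medication use, have been run by coded group.* CRP and medication use need naming because they appear in neither Table 2 nor Table 3.

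In section 1, replace the sentence on secondary outcomes with: *This plan governs the 6-month secondary outcomes of section 2.8 as specified in section 4.5. Separate plans cover only other outcomes or time points, and each states its date relative to unblinding.*

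Exempt the per-protocol analyses. Both populations in section 3.1.2 are defined by arm, so they cannot be formed without knowing which group is which.

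Unblinding need not wait for every separate plan to be signed. Some may concern unrelated outcomes, and stating their date relative to unblinding is enough for a reader to judge them.

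The cost is a few sentences and a short delay in unblinding while the remaining 6-month comparisons are run. No new data are needed, and the primary analysis and sample size do not change.

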## 2.5 Data collection

At baseline, data were collected on demographic factors, lifestyle and medical history. Current age and lifestyle information such as smoking were self-reported by the participant through questionnaires.

Information on dietary quality was collected by an abbreviated food frequency questionnaire (FFQ), consisting of questions about the habitual food intake of the last month (12). This FFQ was used to assess the Dutch Healthy Diet Index which examines adherence to the Dutch Dietary Guidelines. For each component of the dietary guidelines, patients received score ranging from 0 to 10, leading to a total score from 0 to 160 with higher scores indicating better adherence. More information about the Dutch Healthy Diet Index is described elsewhere (13).

Physical activity was assessed using the Short Questionnaire to Assess Health-enhancing physical activity (SQUASH). Participants were asked about physical activity during commuting, activities at work/school, household activity and leisure time activity including sports in a usual week during the past month in days per week, and hours and minutes per day (14). Data from the SQUASH was used to calculate minutes per week moderate to vigorous physical activity (MVPA). The intensity of the specific activities is based on a combination of metabolic equivalent (MET) scores according to the compendium of Ainsworth (15) and self-reported intensity. Activities with a MET score of  $\geq 4.0$  or  $\geq 3.0$  were scored as MVPA for participants younger than 55 years and participants of 55 years and older respectively.

Self-reported medication of the participants was coded according to the Anatomical Therapeutic Chemical Classification System (ATC). The summary of cardiovascular medication use will include the following drugs, ordered by ATC code:

- B01 Antithrombotic agents
- C02 Antihypertensives
- C03 Diuretics
- C07 Beta-blocking agents
- C08 Calcium-channel blocking agents
- C09 Agents acting on the renin-angiotensin system
- C10 Lipid lowering
- C10AA Statins

Results will be shown as proportion of patients taking lipid lowering agents (C10), antiplatelet or anticoagulant agents (B01) or blood pressure lowering agents (C02 + C03 + C07 + C08 + C09).

Information about the type of cardiovascular disease and time since the last cardiovascular event were retrieved from electronic patients records. Type of CVD was classified according to the following (non-mutually exclusive) CVD types:

- Coronary Artery Disease
- Cerebrovascular Disease
- Aortic Aneurysm
- Peripheral Artery Disease
- Other

In case people fall into the high-risk category but cannot be classified into one of the four diseases, they are classified as Other.

During a study visit, subjects were physically examined by a trained researcher in the hospital and a nurse obtained a blood sample. Physical examination included measurement of body weight (kg) and height (cm) with the subject wearing indoor clothing. If people were weighed wearing shoes, the weight was subtracted with 1.5 kg to correct for this. Body mass index was computed by dividing the weight in kilograms by height in meters squared. Waist circumference was measured at the midpoint between the bottom rib and the top of the hipbone. Systolic and diastolic blood pressures were

measured with the subject seated, after a 5-minute rest. Measurements were performed trice on the non-dominant upper arm with an automatic device (Microlife WatchBP home A) and values were averaged. Venous blood was drawn for the assessment of serum lipids and biomarkers of nutritional intake. Besides, participants were asked to collect 24-hour urine samples for determination of sodium, potassium and albuminuria.

All measurements were repeated after 3, 6 and 12 months. For the analysis of the primary results, only the 6-month measurements will be used.

## 2.7 Primary endpoints

The primary outcome of this study is change in 10-year CVD risk as predicted with the SMART risk score (10). The SMART risk score is a model to estimate 10-year recurrent cardiovascular risk expressed as percentage and to predict the effect of treatments such as smoking cessation, blood pressure lowering or lowering LDL-cholesterol (10). To assess the SMART risk score at baseline, we will use the model as shown in figure 1 below and described in (10). The model considers age (y), time since last cardiovascular event (y), type of CVD, having diabetes (y/n) smoking status (y/n), total cholesterol (mmol/l), high-density lipoprotein cholesterol (mmol/l), low-density lipoprotein cholesterol (mmol/l), triglycerides (mmol/l), C-reactive protein (CRP, mg/L), systolic blood pressure (mmHg), estimated Glomerular Filtration rate (eGFR) and anticoagulant (ATC code B01) use to estimate the 10-year recurrent cardiovascular risk. For type of CVD, the original formula includes factors for four different CVDs (coronary artery disease, cerebrovascular disease, aortic aneurysm and peripheral artery disease). For other CVDs, a factor representing the average of the factors associated with these four diseases is used.

*Figure 1 Calculation of 10-year CVD risk according to the SMART risk score*

10-year CVD risk (%) =  $(1 - 0.81066^{\exp(\text{linear predictor} + 2.099)}) \times 100\%$

In which Linear predictor =

```
-0.0349602236 * age +  
0.0005510715 * age^2 +  
ifelse(sex=="M", 0.2876587433, 0) +  
0.3455832714 * isSmoking +  
0.0018913154 * sbp +  
0.3181706587 * diabetesDiagnosis +  
0.2947019539 * coronaryArteryDisease +  
0.3483178604 * cerebrovascularDisease +  
0.3303566308 * aorticAneurysm +  
0.2244665798 * peripheralArteryDisease +  
0.2994607562 * otherDisease +  
0.0476995851 * yearsSinceFirstDiagnosis -  
0.0016497342 * yearsSinceFirstDiagnosis^2 +  
0.5403642493 * log(nonHdl) -
```

0.0396752081 * egfr +
0.0002186126 * egfr^2 +
0.1517601731 * log(crp) -
0.2107210313 * usingAnticoag

To estimate the change in 10-year risk during the 6 months of the study, we will consider changes in LDL cholesterol and systolic blood pressure as these are causal risk factors known to be influenced by diet (16, 17). With the SMART risk model, the effect of changes in these risk factor can be estimated by using a Hazard Ratio (HR) related to these risk factors (10). Every decrease of 1.0 mmol/L in LDL-cholesterol is shown to reduce an individual's cardiovascular risk with 20%, corresponding to an HR of 0.80 (18). Per decrease of 10 mmHg for systolic blood pressure, cardiovascular risk is estimated to be reduced with 22%, hence a HR of 0.78 is used (19). Multiplying the effects of the changes in LDL-cholesterol and systolic blood pressure with the baseline risk, gives us the predicted change in 10-year risk at the end of the intervention.

In short, 10-year CVD risk at six months is calculated as  $10\text{-year CVD risk at baseline} * (0.78^{\text{LDL-c end} - \text{LDL-c baseline}}) * (0.8^{(\text{SBP end} - \text{SBP baseline})/10})$ . By subtracting the 10-year CVD risk at six months from the 10-year CVD risk at baseline, the change in SMART risk score will be calculated.

*Table 1 Example calculation of 10-year CVD risk at six months using changes in LDL-cholesterol and systolic blood pressure*

Baseline risk	Change in LDL-c	Change in SBP	6 months risk	Change in risk
1%	increased with 1mmol/l	increased with 3 mmHg	$1 * (0.78^{-1}) * (0.8^{3/10}) = 1.2\%$	+0.2%
20%	decreased with 1mmol/l	decreased with 5 mmHg	$20 * (0.78^1) * (0.8^{5/10}) = 13.9\%$	-6.1%
20%	decreased with 0.5 mmol/l	decreased with 2 mmHg	$20 * (0.78^{0.5}) * (0.8^{2/10}) = 17.3\%$	-2.7%
80%	no change	increased with 1 mmHg	$80 * (0.78^0) * (0.8^{1/10}) = 80.9\%$	+0.9%

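### Hazard ratios are multiplied onto a cumulative 10-year risk instead of the hazard, so changes in the primary outcome are overstated and 6-month risks can exceed 100%

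*SAP*

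**What the plan says.** All of this is in SAP section 2.7.

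- The SMART score is introduced as a "model to estimate 10-year recurrent cardiovascular risk expressed as percentage". Figure 1 gives its form as "1 - 0.81066^{\exp(\text{linear predictor} + 2.099", closed with brackets and multiplied by 100%. This is a cumulative risk from a proportional-hazards model.
- For the 6-month value, the section says the effect of risk-factor changes "can be estimated by using a Hazard Ratio (HR) related to these risk factors (10". For LDL it takes a 20% reduction per 1.0 mmol/L, "corresponding to an HR of 0.80 (18"; for SBP a 22% reduction per 10 mmHg, "hence a HR of 0.78 is used (19".
- It then forms the 6-month risk by "Multiplying the effects of the changes in LDL-cholesterol and systolic blood pressure with the baseline risk". The formula multiplies the baseline percentage by "0.78^{\text{LDL-c end} - \text{LDL-c baseline}}) * (0.8^{(\text{SBP end} - \text{SBP baseline})/10", and Table 1 works four examples as products, one of them from a baseline of 80%.

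The SAP gives no transformation to the hazard scale and no upper limit at 100%.

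**The concern.** A hazard ratio multiplies the event rate, not the 10-year probability. The two operations nearly agree when risk is small and part company as it grows, because a probability is bounded at 1 and a rate is not. The section therefore uses one model for the baseline risk and an incompatible operation for the 6-month risk.

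The operation sets the primary outcome of every patient whose LDL or SBP changes. It enlarges falls and rises alike, most of all in high-risk patients. If the intervention works, the absolute between-arm difference is reported too large and the outcome's spread is inflated. In patients at high risk who worsen, the result may not be a probability at all.

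**Working it through.** **Inputs.** From section 2.7: the form of Figure 1, HR 0.80 per 1 mmol/L LDL decrease, HR 0.78 per 10 mmHg SBP decrease, and the Table 1 examples. From section 2.9: design difference 3.3 points, SD 6.3 points. Other inputs are marked as assumed.

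**1. The plan's own figures.** Evaluating the Table 1 expressions as printed:

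| Row | Expression | Result | Stated |
|---|---|---|---|
| 1 | 1 × 0.78^(−1) × 0.8^0.3 | 1.20 | 1.2 |
| 2 | 20 × 0.78 × 0.8^0.5 | 13.95 | 13.9 |
| 3 | 20 × 0.78^0.5 × 0.8^0.2 | 16.89 | 17.3 |
| 4 | 80 × 0.8^0.1 | 78.24 | 80.9 |

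Rows 1 and 2 confirm that the product is what is computed. Rows 3 and 4 do not follow from their own expressions. Dividing SBP by 20 instead of 10 gives 17.27 and, with the sign turned in row 4, 80.90. The hazard-scale rule with the HRs as in the text happens to give 17.30 for row 3, but 14.59 for row 2 and 80.79 for row 4, so it is not the rule behind the table.

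**2. The hazard-scale rule.** Figure 1 implies 1 − R0 = S^exp(LP), with S = 0.81066 and LP including the constant. Multiplying the hazard by HR gives survival S^(HR × exp(LP)) = (1 − R0)^HR. Hence

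R6 = 1 − (1 − R0)^HR, where the SAP has R6 = R0 × HR.

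**3. Direction.** By Bernoulli's inequality, R0 × HR < 1 − (1 − R0)^HR when HR < 1, and the reverse when HR > 1. The product is always further from R0. A grid over R0 = 1–99% and HR = 0.30–3.00 showed no exception. For a given HR this does not depend on which coefficient belongs to which risk factor.

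**4. Size per patient at HR 0.80.**

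| R0 | Product | Hazard scale | Change: product vs hazard scale | Ratio |
|---|---|---|---|---|
| 20% | 16.0 | 1 − 0.8^0.8 = 16.35 | −4.0 vs −3.65 | 1.10 |
| 40% | 32.0 | 1 − 0.6^0.8 = 33.55 | −8.0 vs −6.45 | 1.24 |
| 80% | 64.0 | 1 − 0.2^0.8 = 72.41 | −16.0 vs −7.6 | 2.1 |

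For small changes the overstatement factor is R0 / [−(1 − R0) ln(1 − R0)]: 1.01 at 1%, 1.05 at 10%, 1.12 at 20%, 1.44 at 50%, 2.49 at 80%.

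The Table 1 patients, with the text's HRs and signs set right (product vs hazard scale): row 1 +0.347 vs +0.344; row 2 −5.87 vs −5.41; row 3 −2.98 vs −2.70; row 4 +2.01 vs +0.79.

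**5. Values above 100%.** These need HR > 1/R0: 5 at 20%, 1.67 at 60%, 1.25 at 80%. At R0 = 80%, a 10 mmHg rise gives 80/0.78 = 102.6% (hazard scale 87.3%). Adding a 1 mmol/L LDL rise gives 80/(0.78 × 0.80) = 128.2% (hazard scale 92.4%).

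**6. Between-arm difference.** Simulation with an assumed effect of −0.3 mmol/L LDL and −4 mmHg SBP, assumed SDs of individual change of 0.5 and 12, and HRs as in the text:

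| Mean baseline risk | Product | Hazard scale |
|---|---|---|
| 21% | −3.37 | −2.89 |
| 31% | −5.04 | −3.90 |
| 74% | −11.8 | −5.3 |

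At 74%, 18% of controls exceed 100%. Repeating this with other assumed spreads of baseline risk gave −3.36 to −3.47 vs −2.84 to −2.94 near 21%, and −11.7 to −11.8 vs −5.0 to −5.1 near 74%. The SD of individual change near 21% was 7.9 vs 6.3 points.

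**7. Which baseline range applies.** Figure 1 as printed gives 74% for a man and 64% for a woman aged 68 with coronary disease. Only the age comes from the SAP (section 5); assumed are SBP 135, non-HDL 2.6, eGFR 75, CRP 1.5, 3 years since diagnosis, B01 use, non-smoker, no diabetes. Without the +2.099 term the same patients have 15% and 12%.

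**The case against.** The algebra is not in dispute; the counter-case concerns meaning and impact.

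- **Risk ratios may have been meant.** The section also describes the effects as 20% and 22% reductions in risk. If the cited sources report ratios of cumulative risk, multiplication is coherent for decreases and the label is what is wrong. The sources are not at hand. But the SAP names the hazard ratio as its method and labels both numbers so, and even as risk ratios the rule can pass 100% when risk factors worsen.
- **The hypothesis test is nearly unaffected.** This stands. With 57 per arm, the planned ANCOVA without the hospital term and the effects assumed above, type I error was 4.4–5.2% on both scales. Power (product vs hazard scale) was 69% vs 72% at mean baseline 21%, 70% vs 74% at 31% and 76% vs 77% at 74%. Effect and spread grow together, so no false positives are created.
- **At ordinary risk the error is modest.** This stands too: about 8–12% of a patient's change at 20%, and at most 0.4% of controls above 100% at mean baselines of 15–31%.
- **The largest figures depend on the Figure 1 constant.** Correct. The 74% scenario is conditional on +2.099 being right, which the SAP alone cannot settle.
- **Other errors come first.** Taken literally, the formula's end-minus-baseline exponents reverse the direction (row 2 gives 28.7%), and row 1 of Table 1 is printed as +0.2 against about +0.35. The overstatement describes the rule with its signs set right, not every printed figure.

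**Conclusion.** The concern holds. By the SAP's own baseline model and its own label for 0.80 and 0.78, multiplying them onto the risk percentage is the wrong operation, and it exaggerates every non-zero change once the direction is set right. The excess is about 10% of a patient's change at 20% baseline risk, 24% at 40% and 2.1-fold at 80% (HR 0.80). The per-patient results are exact. The between-arm results rest on the assumed effects, SDs and baseline distributions; under these, at a mean baseline near 21%, the product and hazard-scale differences fall on opposite sides of the 3.3-point design difference. The harm is to the reported absolute effect, its spread and the validity of individual values, with little effect on the p-value. It must be fixed because it defines the primary outcome.

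**What to change.** Replace the 6-month formula in section 2.7 with

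risk at 6 months (%) = 100 × [1 − (1 − baseline risk/100)^(HR_LDL × HR_SBP)],

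where HR_LDL = 0.80^(LDL baseline − LDL 6 months) and HR_SBP = 0.78^((SBP baseline − SBP 6 months)/10). This form also carries the HR assignment given in the text and the right signs. Confirm in the cited sources that 0.80 and 0.78 are hazard ratios, and say so.

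Recompute all four rows of Table 1. Before coding, check the +2.099 constant in Figure 1 against the source model, since it decides whether typical baseline risk is near 15% or near 74%. Check that the 3.3-point difference and 6.3-point SD in section 2.9 refer to the same scale.

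The cost is one SAP formula, one line of code, the recomputed table and these checks. No new data are needed, and the change can be made before the group codes are broken. The reported effect will be somewhat smaller.
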